#### **Design**

This will be a double blinded, randomized controlled, clinical trial (therapy, level 1B). The principal investigator (PI) will be blinded to the group assignment as it will be performed by a research assistant who will be trained for the group allocation. A flow diagram according to the Consolidated Standards of Reporting Trials (CONSORT) statement will be presented to illustrates the progression of this clinical trial (**Schulz et al., 2010**). Also, this trial will be registered at one of the clinical trial registries.

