## Subjects:

Sixty-six male and female patients, with age between 20-50 years, diagnosed with SIS will be recruited through direct referrals, thus, a sample of convenience will be used. They will be asked to sign the informed consent

form (**Appendix I**). Participants will be randomly allocated to three experimental groups as follow:

**Group A** (n=22): will receive a program of scapular muscle strengthening exercises for 18 sessions (3 sessions per week for six weeks)

**Group B** (n=22): will receive a scapular PNF exercise program for the same frequency as in group A

**Group C** (n=22): will be a control group who will not receive any treatment during the study period.

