## **Shoulder pain and disability index (Appendix II):**

Self-report questionnaire developed to measure the pain and disability associated with shoulder pathology. The SPADI consists of 13 items in two subscales: pain (five items) and disability (eight items).

The pain dimension consists of five questions regarding the severity of an individual's pain. Functional activities are assessed with eight questions designed to measure the degree of difficulty an individual has with various activities of daily living that require upper-extremity use. The SPADI takes 5 to 10 minutes for a patient to complete and is the only reliable and valid region-specific measure for the shoulder **(Roash al., 1991)**.

Patients asked to mark the appropriate point on the scoring system of the questionnaire, which represented their status of shoulder pain and disability. Total pain score:  $/ 50 \times 100 = \%$ , Total disability score:  $/ 80 \times 100 = \%$  and Total SPADI score:  $/ 130 \times 100 = \%$  Higher score on the SPADI is indicative of higher pain and/or disability **(Breckenridge al., 2011)**.

Psychometric Properties the SPADI :MDC: 18 point (MDC 95%) with  $ICC \geq 0.89$ , The MCID has been reported to be 8 points; this represents the smallest detectable change that is important to the patient **(Paul et al 2004)**.

No large floor or ceiling effects for the SPADI have been observed **(Bot et al 2004, Roy et al 2009)**.

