## **Treatment procedure**

[figure not shown]
Group (A) will have scapular muscle training and group (B) will have a scapular PNF program and Group (C) will be a control group will not receive any treatment. Both groups A and B will receive 18 therapy visits (3 sessions per week for 6 weeks).

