### **Group (A) Scapular muscle strengthening**

The following four exercise will be performed according to **Cools et al. (2007)**: (1) side-lying forward flexion, (2) side-lying external rotation, (3) prone horizontal abduction with external rotation, and (4) prone extension in neutral position (**Figure 21**).

Before starting the program, the patient will be thoroughly instructed in the four exercises, and illustrations with specific exercise instructions will be provided, as well as a compliance log. All subjects will perform the exercises with the affected side for three sets of 10 repetitions for each exercise, with a 1-minute rest between sets. The exercises are described in (**table 1**)

**Figure 15** the proposed scapular strengthening program

[figure not shown]
**Table 1.** Description of the scapular training program

Exercise	Description
Prone extension	The subject is prone with the shoulders resting in 90 of forward flexion. From this position, the subject performs bilateral extension to a neutral position with the shoulder in neutral rotation.
Forward flexion in side lying	The subject is in a side-lying position, with the shoulder in neutral. The subject performs 90 of unilateral forward flexion in a sagittal plane.
External rotation in side lying	The subject is side lying with the shoulder in neutral position and the elbow flexed 90. From this position, the subject performs 90 of external rotation of the shoulder with a towel between the elbow and trunk to avoid compensatory movements.
Prone horizontal abduction with external rotation	The subject is prone with the shoulders resting in 90 of forward flexion. From this position, the subject performs bilateral horizontal abduction to a horizontal position, with an additional external rotation of the shoulder at the end of the movement.

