## **Group (B) Proprioceptive neuromuscular facilitation (PNF)**

In the PNF group, scapular PNF will be applied by a trained therapist in two diagonals, anterior elevation and posterior depression (Fig. 22A and 22B, respectively) and posterior elevation and anterior depression (Fig. 22C and 22D, respectively) for three sets of 10 repetitions, The rest interval between repetitions will be 20 seconds (Mtaspinar et al., 2013; Park et al., 2008).

[figure not shown]
**Figure 16 A) Anterior elevation of the scapula, B) posterior depression of the scapula, C) posterior elevation of the scapula, D) anterior depression of the scapula**

Patients will lay on the unaffected side while the therapist stands in the line of desired motion. Firstly, the therapist will give preparatory instructions. In the beginning of the pattern, the therapist pulls the scapula to the elongated position and then gives instructions for the desired movement.

Rhythmic initiation and repeated contractions facilitation techniques will be applied in all patterns. The rhythmic initiation technique teaches the motion, helps the patient to relax, improves coordination, and normalizes the motion. The repeated contractions technique increases active range of motion and strength and guides the patient's motion towards the desired motion. (Mtaspinar et al., 2013; Park et al., 2008). Description of each scapular PNF pattern is described below

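### The protocol calls the trial double blinded but names only one blinded party, and its untreated control arm means the label cannot carry its usual sense of blinded patients

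*Protocol*

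**What the plan says.** The Design section of the protocol states: "This will be a double blinded, randomized controlled, clinical trial (therapy, level 1B). The principal investigator (PI) will be blinded to the group assignment". The reason it gives for the principal investigator's blinding is that "it will be performed by a research assistant who will be trained for the group allocation". It mentions no other blinded role.

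On the arms:

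- **Group C:** the Subjects section says it "will be a control group who will not receive any treatment during the study period", and the Treatment procedure section repeats this: "Group (C) will be a control group will not receive any treatment". No sham or attention control is described.
- **Groups A and B:** "Both groups A and B will receive 18 therapy visits", at three per week for six weeks.
- **Group A:** patients are taught four exercises, and "illustrations with specific exercise instructions will be provided, as well as a compliance log".
- **Group B:** "scapular PNF will be applied by a trained therapist in two diagonals".

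Pain and function are measured by SPADI, described as a "Self-report questionnaire developed to measure the pain and disability associated with shoulder pathology". Muscle strength (hand-held dynamometer) and scapular position (lateral scapular slide test) are measured by an examiner whose relation to the principal investigator is not given.

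**The concern.** Double blinding normally tells a reader that at least two parties are masked, and that patients are one of them. The Design section accounts for one party, the principal investigator. The only other person it mentions performs the group assignment and so knows it.

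What is at stake is how the outcomes are read. If the label is taken at face value, patient-reported pain and function look protected against expectation effects. In the design as described they are not, at least where a treated group is compared with patients who know they have had no treatment. The Statistical analysis section compares all three groups, so those contrasts form part of the planned analysis.

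The examiner-measured outcomes raise a related question: the text does not say whether the person taking the measurements is masked to group.

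**Working it through.** No calculation bears on this point, since it does not depend on alpha, power or effect size. The check takes each role in turn and asks what the protocol says about its blinding and whether the described procedures allow it.

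- **Principal investigator.** Stated to be blinded (Design). The reason given covers only who makes the allocation. No part in treatment, measurement or analysis is assigned to the principal investigator, and no means of staying masked through the after-treatment assessment is described.
- **Research assistant.** Performs the allocation (Design), so is not blinded.
- **Group C patients.** No treatment and no sham (Subjects; Treatment procedure). They cannot be blinded to being untreated.
- **Group A and B patients.** Each receives an active programme, and the two differ visibly: self-performed exercises with a log against manual PNF. They know what they are doing. Whether they know what the other active arm is doing depends on the consent text, which is not available here.
- **Therapist in group B.** Applies the patterns by hand, so must know the arm.
- **Examiner.** Blinding status not stated. In the dynamometer procedure the examiner does not look at the readout until the test is over. That masks the reading, not the group.
- **Analyst.** Not mentioned.

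Count: one role is stated to be blinded; group C patients and the group B therapist cannot be; the examiner (if not the principal investigator) and the analyst could be, but are not stated to be.

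Therapy contact per patient:

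- A: 3 per week × 6 weeks = 18 visits
- B: 3 per week × 6 weeks = 18 visits
- C: 0 therapy visits, although these patients are still assessed twice

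Consequences by outcome:

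1. **SPADI.** The patient circles the scores, so the patient is the assessor. In A versus C and B versus C, one side of the comparison knows it was untreated. These contrasts are unblinded whoever hands out the form.
2. **Strength.** The dynamometer captures the greatest force the subject produces, and the examiner matches that effort. Both patient effort and examiner technique enter the reading. Masking the examiner deals with the second only.
3. **Scapular slide.** The examiner palpates and marks the landmarks, then measures with a caliper. Examiner masking matters directly here.

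**The case against.** The strongest reply is that the arms do not exclude a second blinded party. A masked examiner separate from the principal investigator, or a masked analyst, would make two, and nothing in the treatment descriptions prevents either. This stands. A reader might infer that double blinding of any kind is ruled out, but the documents support only that it is unexplained, and that it fails in the usual sense of blinded patients.

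A second reply is that the hypotheses do not involve group C. All twelve compare strengthening with another exercise programme: PNF in ten, motor control exercise in items 9 and 10. This stands in part. Both active arms have 18 visits, so differential expectation between A and B is likely smaller, and how large cannot be judged without the consent text. It would go too far to call every SPADI comparison equally compromised. But the planned analysis covers three groups, so contrasts with C will be available and are the most exposed.

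A third reply is that a blinded principal investigator may be the examiner, in which case strength and scapular position would be protected. The protocol does not say so. Even if it did, strength depends on the effort of a patient who may know that he or she is untreated, and patients can disclose their group. Masking would reduce bias in these outcomes, not remove it.

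Finally, blinding patients is hard in exercise trials. That is a reason to drop the label, not to keep it.

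**Conclusion.** The concern holds as a mismatch between label and description. The protocol claims double blinding, identifies one blinded party, and describes a control arm whose patients cannot be blinded to receiving nothing. SPADI contrasts with group C are therefore unblinded. The blinding of the strength and scapular slide measurements is undetermined on the text.

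No magnitude of bias can be derived from the document and none is claimed. The observable difference is 18, 18 and 0 therapy visits per patient in A, B and C. The conclusion assumes that no sham exists beyond what is described. It does not depend on the consent wording for group C, since no wording could hide the absence of treatment. For A versus B it does, and the effect there stays open.

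This is not something to leave to a statistical analysis plan. Who is blinded is a design statement that the protocol already makes. The correction is worth making because it changes what a reader may conclude from the patient-reported outcomes, although it is mainly a matter of wording.

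**What to change.** Replace the double-blind label in the Design section with a statement for each role:

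- Patients and treating therapists are not blinded.
- SPADI pain and function are unblinded self-report, and contrasts with group C are to be read in that light.
- Dynamometer and scapular slide measurements are taken by someone already masked to group, with patients asked not to reveal their group. This could be the principal investigator, provided he or she neither treats nor allocates; the protocol does not yet give the principal investigator that task.
- If no masked examiner is available, make no claim of assessor blinding.
- If the analyst is to be masked, say so.

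No sham arm is asked for. The cost is protocol wording and a less favourable blinding label. A masked examiner would be needed for up to 66 after-treatment assessments, or 66 × 2 = 132 sessions if the before-treatment assessments are also covered and nobody drops out. Whether this needs extra staff depends on the principal investigator's role, which the protocol leaves unstated.

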#### **Randomization:**

Patients will be randomly assigned into one of the three groups. We will use a simple randomization method to allocate participants to the groups. A random number generator available online from [www.randomization.com](http://www.randomization.com) will be used.

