## Sample size calculation:

In order to detect an effect size of Cohen's  $d = 0.80$  with 80% power ( $\alpha = 0.05$ ), G\*power software (version 3.1.9.7; Franz Faul, Universitat Kiel, Germany) suggests we will need 64 participants, however, we will aim to recruit 66 subjects to have equal groups representation (22 per group) using analysis of variance (ANOVA) test as shown in the (figure 7).

[figure not shown]

Figure 1 ample size calculation

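### Simple randomization will almost certainly not give the stated 22 patients per group (1.2% chance); a permuted-block list built to total 66 would

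*Protocol*

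**What the plan says.** The Randomization section of the protocol states that "Patients will be randomly assigned into one of the three groups" and then that "We will use a simple randomization method to allocate participants to the groups". The numbers are to come from an online generator. No blocks, strata or limit on group size are mentioned.

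The Sample size calculation section reports that the software "suggests we will need 64 participants" and continues: "we will aim to recruit 66 subjects to have equal groups representation (22 per group) using analysis of variance (ANOVA) test". Equal group size is the only reason given for the two additional patients.

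The Subjects section then gives a size for each group, with no word such as *about* or *expected*:

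- Strengthening (A): "n=22): will receive a program of scapular muscle strengthening exercises for 18 sessions"
- PNF (B): the size is again given flatly as 22.
- Untreated control (C): "n=22): will be a control group who will not receive any treatment during the study period"

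**The concern.** In simple randomization each patient is assigned independently, here with probability 1/3 to each group. Nothing in that process pulls the totals towards 22. The protocol therefore fixes both a method and a result, and the method will rarely produce the result.

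The person who makes the assignments cannot count on satisfying both sections. Following the Randomization section will almost always break the group sizes in the Subjects section, and the trial's CONSORT flow diagram will show the difference. If staff instead closed each group once it reached 22, which the protocol does not say they will do, the method would no longer be simple randomization and the last assignments would be known in advance.

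Bias is not at stake. At stake are the stated purpose of going from 64 to 66, a little power, and a clear instruction for allocation.

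**Working it through.** **Inputs.** Three groups and simple randomization (Randomization section); calculated total 64, planned total 66, 22 per group, 80% power, alpha 0.05, effect size written as d = 0.80 (Sample size calculation section); n = 22 for each group (Subjects section).

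**1. The protocol's own figure.** One-way ANOVA with 3 groups, noncentrality λ = N × f², and 2 and N − 3 degrees of freedom. The protocol does not give f. Assuming f = d/2 = 0.40:

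- N = 63: power 0.798
- N = 64: λ = 64 × 0.16 = 10.24, power 0.805
- N = 66 as 22/22/22: λ = 66 × 0.16 = 10.56, power 0.818

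The smallest N that reaches 80% is 64, as stated. The next multiple of 3 is 66.

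**2. Chance of exactly 22 per group.** Multinomial with N = 66 and p = 1/3:

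P(22/22/22) = 66! / (22!³ × 3⁶⁶) = 0.0124, or 1.2%. The chance of unequal groups is 98.8%.

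**3. How unequal.** Each group size has mean 66/3 = 22 and standard deviation √(66 × 1/3 × 2/3) = 3.8. Enumerating every split of 66 gives:

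| Quantity | Value |
|---|---|
| Expected smallest group | 18.1 |
| P(some group ≤ 17) | 35.0% |
| P(some group ≤ 16) | 21.7% |
| Largest minus smallest, mean | 7.9 |
| Largest minus smallest, median | 8 |
| P(largest minus smallest ≥ 5) | 78.9% |
| P(largest minus smallest ≥ 10) | 32.3% |

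**4. Effect on power.** Averaging the power at f = 0.40 over the multinomial group sizes gives 0.809. The result is the same to three decimals whether the three means are evenly spaced or one group differs from the other two.

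- Gained by going from 64 to 66 with equal groups: 0.818 − 0.805 = 0.013
- Lost on average through unequal groups: 0.818 − 0.809 = 0.009

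So about 0.9 of the 1.3 percentage points gained is lost on average.

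**5. If groups were closed at 22.** In 20,000 simulated sequences, an average of 4.2 assignments at the end had only one group left open and were therefore fully determined.

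**6. Check of the remedy.** Six blocks of 3 and eight blocks of 6 total 6 × 3 + 8 × 6 = 66, and each group receives 6 × 1 + 8 × 2 = 22. All of 20,000 simulated lists gave 22/22/22. In the 3,000 lists also checked step by step, the difference between groups never exceeded 2 at any point in recruitment.

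Its predictability, if every block boundary were known:

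- Block of 3: the last assignment is determined, so 1.0.
- Block of 6: the last is determined, and the one before it too when the final two are the same (probability 1/5), so 1 + 1/5 = 1.2.
- Total: 6 × 1.0 + 8 × 1.2 = 15.6 of 66. Fixed blocks of 3 would give 22 of 66.

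The blocks must be chosen to fill 66. Block sizes 3, 6 and 9 drawn at random without that condition gave 22/22/22 in only 67% of lists.

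**The case against.** The best case for leaving the text alone has four parts.

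- **22 is a target.** The Sample size calculation section speaks of an aim, and rounding 64 up to a multiple of 3 is ordinary planning arithmetic. This is fair for that section. It does not cover the Subjects section, which gives n=22 for each group outright.
- **The word *simple* may be loose.** If it meant only that there are no strata or blocks, a single random ordering of 66 labels, 22 per group, would satisfy all three sections. The protocol does not say so, and independent assignment is the usual meaning. If a balanced list was intended, the Randomization section still needs correcting.
- **The harm is small.** This stands. Exact equality is a strict criterion, missing it causes no bias, and average power of 0.809 is still above 80%. Individual allocations can do worse: at f = 0.40, between 35% and 38% of them fall below 80% power, depending on the pattern of means. The closed-group scenario is hypothetical and carries little weight.
- **Blocks bring a risk of their own.** In an exercise trial with an untreated group, assignments are visible, so staff who know the block boundaries can predict some of them. Simple randomization has no such weakness. A single random permutation of 66 labels would also guarantee 22 per group, with only about 1.5 determined assignments at the end. This is a real alternative; what it lacks is the blocks' control of balance if recruitment stops before 66.

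These points limit the weight of the concern and widen the choice of remedy. They do not remove the conflict between the sections.

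**Conclusion.** The concern holds. As written, the protocol states a group allocation that its own method gives about once in 80 trials (1/0.0124 ≈ 81). The probabilities for group size rest only on the literal reading of simple randomization with equal probabilities and on exactly 66 patients being randomized. The power figures rest in addition on f = 0.40, which is an assumption, although it reproduces the stated 64.

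The inconsistency is certain and its statistical cost is modest. It should be corrected before the first patient is allocated, but it would not invalidate the trial.

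**What to change.** Replace the sentence on the method in the Randomization section with, for example:

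> Participants will be allocated 1:1:1 using a pre-generated list of randomly permuted blocks of sizes 3 and 6 in random order, with the blocks totalling exactly 66 (six blocks of 3 and eight blocks of 6; 22 per group). The list and the block sizes will be concealed from recruiting and assessing staff.

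This gives 22 per group once all 66 are enrolled. The cost is one sentence and one list made in advance. The drawback is the within-block predictability shown above; mixing the sizes in random order and concealing the list limits it. A single concealed permutation of 66 labels, 22 per group, is an acceptable alternative if predictability matters more than balance during recruitment.

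If simple randomization is preferred, keep the Randomization section. In the Sample size calculation and Subjects sections, call 22 the expected group size and no longer give equal groups as the reason for 66. That costs only the rewording.

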## Sample size calculation:

In order to detect an effect size of Cohen's  $d = 0.80$  with 80% power ( $\alpha = 0.05$ ), G\*power software (version 3.1.9.7; Franz Faul, Universitat Kiel, Germany) suggests we will need 64 participants, however, we will aim to recruit 66 subjects to have equal groups representation (22 per group) using analysis of variance (ANOVA) test as shown in the (figure 7).

[figure not shown]

Figure 1 ample size calculation

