### **Hypotheses of the study:**

1. There will be no significant difference between scapular muscle strengthening and PNF exercise on improving muscle strength of upper trapezius in patients with shoulder impingement syndrome.

2. There will be no significant difference between scapular muscle strengthening and PNF exercise on improving muscle strength of middle trapezius in patients with shoulder impingement syndrome.
3. There will be no significant difference between scapular muscle strengthening and PNF exercise on improving muscle strength of lower trapezius in patients with shoulder impingement syndrome.
4. There will be no significant difference between scapular muscle strengthening and PNF exercise on improving muscle strength of serratus anterior in patients with shoulder impingement syndrome.
5. There will be no significant difference between scapular muscle strengthening and PNF exercise on muscle ratio of upper trapezius/lower trapezius muscles in patients with shoulder impingement syndrome.
6. There will be no significant difference between scapular muscle strengthening and PNF exercise on muscle ratio of upper trapezius/middle trapezius muscles in patients with shoulder impingement syndrome.
7. There will be no significant difference between scapular muscle strengthening and PNF exercise on muscle ratio of upper trapezius/serratus anterior muscles in patients with shoulder impingement syndrome.
8. There will be no significant difference between scapular muscle strengthening and PNF exercise on scapular symmetry at 0° abduction in patients with shoulder impingement syndrome.
9. There will be no significant difference between scapular muscle strengthening and motor control exercise on scapular symmetry at 45° abduction in patients with shoulder impingement syndrome.
10. There will be no significant difference between Scapular muscle strengthening and motor control exercise on scapular symmetry at 90° abduction in patients with shoulder impingement syndrome.

11. There will be no significant difference between scapular muscle strengthening and PNF exercise on improving pain in patients with shoulder impingement syndrome.
12. There will be no significant difference between scapular muscle strengthening and PNF exercise on improving function in patients with shoulder impingement syndrome.

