**Figure 20 SCAPULAR ANTERIOR DEPRESSION**

## **Statistical analysis**

- Data will be analyzed using the statistical package for social science (SPSS) program, version 27 (SPSS Inc, Chicago, IL, USA).
- Descriptive statistics will be used to summarize the data. Data will be reported as mean  $\pm$  SD for quantitative variables and frequency distribution (%) for categorical variables.
- The normality of data will be checked using Shapiro–Wilk test.
- Levene’s test will be used to check the homogeneity between groups.
- Two-way Multiple Analysis of Variance (MANOVA) will be conducted to compare the mean values of the measured variables of the three groups.
- The level of significance for all statistical tests will be set at  $\alpha = 0.05$ .

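### The stated 64 participants fit a three-group omnibus effect of f = 0.40, not Cohen's d = 0.80; strengthening versus PNF has about 74% power at d = 0.80

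*Protocol*

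**What the plan says.** The protocol's Sample size calculation section opens with "In order to detect an effect size of Cohen's" d = 0.80, at 80% power and alpha 0.05. It reports that G*Power "suggests we will need 64 participants, however, we will aim to recruit 66 subjects to have equal groups representation (22 per group"), with ANOVA named as the test. The section gives no Cohen's f, standard deviation or outcome. The software figure is not reproduced in the text available.

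The design has three arms: strengthening (A), PNF (B) and a third that "will be a control group who will not receive any treatment during the study period" (Subjects section).

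The purpose, the research question and the hypotheses concern two arms. Hypothesis 11 is typical: "There will be no significant difference between scapular muscle strengthening and PNF exercise on improving pain in patients with shoulder impingement syndrome". Ten of the 12 hypotheses name strengthening versus PNF. Hypotheses 9 and 10 name a different comparator, as in "scapular muscle strengthening and motor control exercise on scapular symmetry at 45° abduction". No hypothesis mentions the control group.

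The Statistical analysis section plans a two-way MANOVA that "will be conducted to compare the mean values of the measured variables of the three groups", with every test at 0.05.

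**The concern.** Cohen's d is the difference between two means in SD units. Cohen's f describes the spread of any number of means. The two are linked by f = d/2 only when there are exactly two equal groups. A sample size that quotes d but uses a three-group ANOVA has therefore either mislabelled its effect size or carried the two-group conversion into a three-group design.

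The hypotheses add to the problem. A reader who sees d = 0.80 with 80% power, next to 12 two-group hypotheses, will take 80% to be the power for strengthening versus PNF. The hypotheses are worded as no significant difference, so a non-significant result is the one most likely to be weighed against that figure. If the true power is lower, such a result is weaker evidence than the protocol implies.

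**Working it through.** **Inputs.** From the protocol: d = 0.80, power 80%, alpha 0.05, ANOVA, three groups, 64 required, 66 planned (22 per group). Assumed: two-sided tests (the hypotheses are non-directional), one outcome at one time point, no dropout, no multiplicity adjustment.

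**1. Reproducing 64.** One-way omnibus F test, k groups, total N: df = (k − 1, N − k), noncentrality λ = N·f², and power is the chance that the noncentral F exceeds the 95th percentile of the central F.

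With k = 3 and f = 0.40:

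| N | λ | Power |
|---|---|---|
| 63 | 10.08 | 0.798 |
| 64 | 10.24 | 0.805 |
| 66 | 10.56 | 0.818 |

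So 64 is the smallest N, an exact match. Other readings do not give it: f = 0.80 with k = 3 gives 19, and a two-sided two-group test at d = 0.80 gives 52 (26 per group). That f = 0.40 was entered is an inference from this match.

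**2. What d = 0.80 implies for f in three groups.** With equal groups, f = √[mean of (μᵢ − μ̄)²] in SD units.

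- Two groups, means ±0.40: f = 0.40 = d/2.
- Three groups, means 0.80, 0, 0: f = √[(0.2844 + 0.0711 + 0.0711)/3] = 0.377. Power at 66 is 76.8%; 80% needs N = 71.
- Three groups, means 0.80, 0.40, 0: f = √[(0.16 + 0 + 0.16)/3] = 0.327. Power at 66 is 63.6%; 80% needs N = 94.

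If 0.80 SD is the largest difference among the three means, omnibus power at N = 66 is therefore 63.6% to 76.8%.

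If 0.80 SD is instead the A–B difference, the control mean may lie outside the A–B range. With means 0.80, 0, −x, 80% at N = 66 needs f = 0.391, which means x of about 0.06. At x = 0.10, f = 0.403 and power is 82.4%.

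**3. Strengthening versus PNF.** Two-sided t test, noncentrality δ = d·√(n/2). With n = 22 and d = 0.80, δ = 0.80 × √11 = 2.653.

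- Two-sample error, 42 df: power 0.736.
- Pooled three-group error, 63 df: power 0.743.
- At 26 per group (50 df): power 0.807. Three such arms total 3 × 26 = 78.
- d giving 80% at 22 per group: about 0.865 (42 df).

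**4. Sensitivity to the analysis model.** The two-way MANOVA could be read as group by time. For a change score, with d on the post-treatment SD, the effect becomes 0.80/√[2(1 − r)], where r is the pre–post correlation (not given in the protocol). Power (42 df) is 64% at r = 0.38, 74% at r = 0.5 and 83% at r = 0.6. For baseline-adjusted ANCOVA the effect becomes 0.80/√(1 − r²), and 80% is reached at r of about 0.38.

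**The case against.** The strongest reply is that the 80% belongs to a three-group ANOVA and the software computed it correctly, so a pairwise power is being compared with an omnibus one. The protocol names no pairwise test, and follow-up comparisons may sit in an analysis plan not seen here. Group C is untreated, so a control mean beyond both active arms is plausible. With A and B 0.80 SD apart, the omnibus test then passes 80% once the control mean is about 0.06 SD outside their range. The 74% also depends on the model: under a group-by-time reading the power can fall on either side of 80%. And the missing figure may simply show f = 0.40.

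Much of this stands. The arithmetic behind 64 is sound, the omnibus shortfall is conditional, and 74% applies to a simple two-group contrast.

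The core is unaffected. The protocol prints d, not f, and no two-sided or ANOVA reading of d = 0.80 returns 64. The condition on the control mean is not stated. The purpose, research question and all 12 hypotheses are two-group contrasts, so the reader will apply the 80% to them. If the figure shows f = 0.40, that confirms where 64 came from and leaves the pairwise power unchanged. An unseen analysis plan cannot make 64 correspond to d = 0.80.

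**Conclusion.** The concern holds. The effect size is mislabelled or wrongly converted; the software calculation itself is not in error. For the effect the protocol names and the comparison its hypotheses make, power is about 74% rather than 80%, a shortfall of about 6 points. This rests on the simple-contrast assumptions listed with the inputs. A change-score analysis moves the figure between 64% and 83% over assumed correlations of 0.38 to 0.6. The omnibus power of 81.8% at N = 66 is right for f = 0.40, but d = 0.80 in three groups does not by itself imply that f.

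This should be corrected, but it does not threaten the trial's design.

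**What to change.** Keep 66 participants. In the Sample size calculation section, remove the statement that 64 corresponds to d = 0.80 and replace it with wording such as:

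> 66 participants (22 per group) give about 82% power for a three-group omnibus effect of f = 0.40. For the strengthening-versus-PNF comparison, 22 per group gives about 74% power at d = 0.80 and 80% power at d of about 0.865 (two-sided alpha 0.05, single outcome, no multiplicity adjustment, no dropout).

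Quote a baseline-adjusted power (80% if the pre–post correlation is at least about 0.38) only if ANCOVA is also written into the Statistical analysis section.

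The cost is a few sentences and a less favourable stated power for the main comparison. No patients are added.

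A separate, minor point: the Randomization section says "We will use a simple randomization method to allocate participants to the groups", which does not guarantee the fixed 22 per group. A concealed permuted-block list with block sizes in multiples of 3 would keep the groups equal. The effect on power is only about one point (73.1% on average against 74.3%).
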